
Patient Population
 
For both phase 1b and phase 2 of the study, eligible patients must have histologically confirmed advanced (locoregionally recurrent, not amenable to curative therapy) or metastatic solid tumors. Please see below for eligibility criteria.
 
Phase 1b Dose Escalation: Patients with locally advanced or metastatic solid tumors.
 
Phase 2 Dose Expansion:
 
The combination cohorts, including patients in the safety-lead phase, will enroll patients with one of the following 3 disease indications:
 
 I. Unresectable/metastatic cutaneous melanoma with primary resistance to no more than 2 prior lines of anti-PD1 containing treatments in the metastatic setting. II. Unresectable/metastatic cutaneous melanoma with acquired resistance to no more than 2 prior lines of anti-PD1 containing treatments in the metastatic setting. III. Unresectable/metastatic cutaneous melanoma naïve to prior anti-PD1 containing treatments in the metastatic setting. 
Please refer to the Eligibility Section for Inclusion and Exclusion details.
	

Number of Patients:
 
Phase 1b Dose Escalation: ~30 patients
 
Phase 2 Dose Expansion: 3 to 9 safety lead-in patients for combination therapy; 25 patients for each expansion cohort (3 cohorts) = ~84 patients.
 
Total: up to ~ 114 patients.
	
Number of Sites:
 
Phase 1b Dose Escalation: approximately 3 to 4 sites.
 
Total number of sites: up to approximately 22.

Dose Level(s):
 
Modakafusp alfa: 0.1, 0.2, 0.4, 0.75, 1.5, 3.0, and 6.0 mg/kg in a 21-day treatment cycle.
 
Pembrolizumab: 400 mg in a 6-week treatment cycle.
	
Route of Administration:
 
Modakafusp alfa: Intravenous (IV)
 
Pembrolizumab: Intravenous (IV)

Duration of Treatment: Patients may receive SA modakafusp alfa for 1 year or modakafusp alfa in combination with pembrolizumab for up to 2 years. Patients with demonstrated clinical benefit can continue treatment beyond this point if approved by the sponsor.
	
Period of Evaluation: The estimated time frame for study completion is 55 months (12 months of enrollment in escalation, 18 months of enrollment in expansion, 24 months of treatment, and 1 month of follow-up).

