8.6.2 Criteria for Beginning or Delaying a Subsequent Treatment Cycle

To begin a new cycle of treatment with either modakafusp alfa alone or in combination with pembrolizumab, the patient must meet the following criteria:

- ANC must be $\geq 1000/\text{mm}^3$. Granulocyte-colony stimulating factor (G-CSF) can be used to reach this level.
- Platelet count must be $\geq 50,000/\text{mm}^3$ without transfusion support.

For therapy to resume, toxicity considered to be related to treatment with modakafusp alfa must have resolved to Grade ≤ 1 or baseline (Grade ≤ 2 for platelets and neutrophils), or to a level considered acceptable by the physician. If the patient does not meet the above-cited criteria for retreatment, initiation of the next cycle of treatment should be delayed for 1 week. At the end of that week, the patient should be re-evaluated to determine whether the criteria for retreatment criteria have been met.

If a subsequent cycle is delayed more than 14 days because of a related AE, the patient may be withdrawn from treatment unless there is clinical benefit as assessed by the investigator, with agreement by the sponsor's medical monitor. Modakafusp alfa dosing may be continued at the previously established safe dose level or below.

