9.3.14 Disease Assessment

At screening, CT and/or MRI scans will be performed unless chest, abdominal cavity, and pelvis diagnostic quality scans were performed within 5 weeks before the planned first dose of study drug. CT and/or MRI scans of the chest, abdominal cavity, and pelvis should be acquired with at least IV contrast. The imaging modalities used for a patient should remain consistent throughout the study. If IV contrast-enhanced CT scans are contraindicated for a particular patient, a noncontrast-enhanced CT of the chest should be acquired in addition to an oral contrast-enhanced CT of the abdomen and IV contrast-enhanced pelvic MRI.

At present, low-dose or attenuation correction CT portions of a combined PET-CT are of limited use in anatomically based efficacy assessments, and it is therefore suggested that they should not be substituted for dedicated diagnostic contrast-enhanced CT scans for anatomically based

RECIST measurements. However, if a site can document that the CT performed as part of a PET–CT is of identical diagnostic quality to a diagnostic CT (with IV and oral contrast), then the CT portion of the PET–CT can be used for RECIST measurements. Note, however, that the PET portion of the CT introduces additional data that may bias an investigator if it is not routinely or serially performed.

Repeat CT and/or MRI scans should be performed every 6 weeks through Cycle 6 and every 9 weeks thereafter, and as clinically indicated.

Response assessment will be calendar-based regardless of treatment delays/interruptions. Investigator assessment of disease response and progression will be based on RECIST v1.1 (Section 9.3.14.1) and iRECIST (Seymour et al. 2017) (phase 2 expansion only). Screening and on-treatment images, when available, should be submitted to the imaging core laboratory vendor for storage and potential retrospective central reading.

In extenuating circumstances, such as during the COVID-19 public health emergency, patients may use an alternative site for imaging with prior notification to the sponsor or designee.

9.3.14.1 *RECIST v1.1 and Treatment Beyond Progression*

Because treatment decisions will be made based on local assessment by the investigator, when assessing response, special consideration should be given to the tumor response characteristics associated with immunotherapy:

1. Measurable tumor size reduction may require a longer treatment duration with immunotherapy than with a cytotoxic regimen.

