- ^t Patients will be followed for survival every 12±1 weeks until death, loss to follow-up, consent withdrawal, or study termination. Survivor information and death details may be collected by methods that include, but are not limited to, telephone, e-mail, mail, or retrieval from online or other databases (eg, Social Security indexes). In addition, the start of another anticancer therapy for the disease under study will be collected.

16.4 Table 16.d Schedule of Events: Screening, Baseline, Cycle 1, Cycle 2, and Cycle 3 (Phase 2 Dose Expansion)

Table 16.d Schedule of Events: Screening, Baseline, Cycle 1, Cycle 2, and Cycle 3 (Phase 2 Dose Expansion)

Study Period or Treatment Cycle	Screening	Cycle 1						Cycle 2		Cycle 3						
		Day <21	Day 1	Day 2	Day 3	Day 4	Day 8	Day 15	Day 1	Day 2	Day 1	Day 2	Day 3	Day 4	Day 8	Day 15
Window Allowed		0	0	0	0	±2 d	±2 d	±2 d	0	±2 d	±0 d	0	0	±2 d	±2 d	
Informed consent ^a	X															
Eligibility criteria	X															
Demographics	X															
Medical history	X															
Prior medication and treatment history	X															
Height (screening only) and weight	X							X		X						
ECOG performance status	X	X						X		X						
12-lead ECG ^b	X	X						X		X						
Triplicate 12-lead ECG ^b		(X)	(X)													
Physical examination	X	X						X		X						
Vital signs ^c	X	X						X		X						
Monitoring of concomitant medication/procedures	Recorded from signing of the ICF through 30 days after last dose of study drug or the start of subsequent anticancer therapy, whichever occurs first.															
AE reporting	Recorded from signing of the ICF through 30 days after last dose of study drug or the start of subsequent anticancer therapy, whichever occurs first. The reporting period for irAEs is extended to 90 days after administration of the last dose of study drug or the start of subsequent anticancer therapy, whichever occurs first, and recorded in the eCRFs.															
	SAEs will be reported from signing of ICF through 30 days after last dose of study drug even if the patient starts nonprotocol systemic therapy. Serious irAEs will be reported through 90 days after last dose of study drug.															
Dosing																
Modakafusp alfa infusion ^d		X							X		X					
Pembrolizumab infusion ^e		X									X					
Disease Assessment																
CT/MRI scans ^f	X	Repeat every 6 weeks through Cycle 6 then every 9 weeks thereafter.														

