- ^f CT and/or MRI scans of the chest, abdominal cavity, and pelvis should be acquired with at least IV contrast. The imaging modalities used for a patient should remain consistent throughout the study. If IV contrast-enhanced CT scans are contraindicated for a particular patient, a noncontrast-enhanced CT of the chest should be acquired in addition to an oral contrast-enhanced CT of the abdomen and IV contrast-enhanced pelvic MRI. At present, low-dose or attenuation correction CT portions of a combined PET-CT are of limited use in anatomically based efficacy assessments, and it is therefore suggested that they should not be substituted for dedicated diagnostic contrast-enhanced CT scans for anatomically based RECIST measurements. However, if a site can document that the CT performed as part of a PET-CT is of identical diagnostic quality to a diagnostic CT (with IV and oral contrast), then the CT portion of the PET-CT can be used for RECIST measurements. Note, however, that the PET portion of the CT introduces additional data that may bias an investigator if it is not routinely or serially performed. Repeat CT and/or MRI scans should be performed every other cycle up to Cycle 7 (Day 1 [-7 days] of Cycles 3, 5, and 7), every 3 cycles thereafter, and as clinically indicated. Response will be determined locally according to RECIST v1.1 (see Section [9.3.14.1](#)). Screening and on-treatment images, when available, should be submitted to the imaging core laboratory vendor for retrospective central reading when it is required. Clinical decisions will be made per local response assessment. Availability of prescreening scan(s) is not a prerequisite for study eligibility (Section [9.3.14.2](#)). If available, the most recent prescreening diagnostic quality CT and/or MRI scans dated within 3 months before the planned first dose of modakafusp alfa should be submitted to the imaging core laboratory vendor for tumor growth rate determination. The date of the scan should be indicated. Response assessment will be calendar-based regardless of treatment delays/interruptions.

- ^g Chemistry will include tests listed in [Table 9.a](#). Chemistry on C1D15 and C3D15 could be assessed in a local hospital if there is no planned PK sampling on those visits per [Table 16.g](#) and [Table 16.h](#).

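### The CT/MRI footnotes anchor scans to cycle Day 1 while also calling assessment calendar-based; once cycles have slipped by more than 7 days in total, no scan date meets both rules

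*Protocol*

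**What the plan says.** The protocol gives the on-treatment scan schedule in three places.

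- **Section 9.3.14:** "Repeat CT and/or MRI scans should be performed every 6 weeks through Cycle 6 and every 9 weeks thereafter", followed by "Response assessment will be calendar-based regardless of treatment delays/interruptions".
- **CT/MRI rows of Tables 16.b to 16.e:** "Repeat every 6 weeks through Cycle 6 then every 9 weeks thereafter".
- **Footnote e (phase 1b) and footnote f (phase 2), which explain those rows:** "Repeat CT and/or MRI scans should be performed every other cycle up to Cycle 7", specified as "Day 1 [-7 days] of Cycles 3, 5, and 7), every 3 cycles thereafter". Each footnote then ends with the calendar statement used in Section 9.3.14.

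Modakafusp alfa is given "in a 21-day treatment cycle". Under Section 8.6.2, when retreatment criteria are not met, "initiation of the next cycle of treatment should be delayed for 1 week". The same section adds: "If a subsequent cycle is delayed more than 14 days because of a related AE, the patient may be withdrawn from treatment". Delays are therefore an expected part of treatment.

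PFS and TTP are dated by first documented progression (Protocol Section 13.4). SAP Section 7.9 reports Kaplan-Meier estimates for both at 3 and 6 months. It also censors at the last non-progressive scan when a patient misses two consecutive assessments; the SAP's summary of changes applies that rule to DOR, PFS and TTP.

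**The concern.** Each footnote contains two clocks. One counts weeks and ignores dosing. The other counts cycles and moves with dosing. The protocol does not say how the Day 1 anchor is to be read when a cycle starts late.

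Three features make the cycle reading a plausible site error:

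- The only on-treatment scan window in the protocol hangs on cycle Day 1. The calendar rule has no window.
- The calendar rule is itself partly cycle-defined, because the change from 6-weekly to 9-weekly scans is placed at the end of Cycle 6.
- After futility, the on-treatment biopsy is set at the end of Cycle 2, up to 7 days before C3D1, to coincide with imaging (Section 9.3.15.2 and footnote y). That pulls the first scan towards the cycle clock.

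At stake is the timing of progression in patients whose cycles are delayed. Many delays reflect toxicity or low counts, so these patients are not a random subset, and sites within one cohort could follow different clocks. The SAP rule on missed assessments also presupposes one nominal schedule, which the SAP does not give.

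**Working it through.** **Inputs.** Cycle length is 21 days (Study Summary). Cycle-rule scans fall at Cycles 3, 5, 7, 10, 13 and so on, with a window of 7 days before Day 1 (footnotes e and f). Calendar scans are every 6 weeks, then every 9 (Section 9.3.14 and table rows). Delay comes in 1-week steps, and delay beyond 14 days for a related AE opens possible withdrawal (Section 8.6.2).

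**1. Reproduce the planned schedule.** Without delay, Day 1 of cycle k falls at week 3(k − 1). Cycles 3, 5, 7, 10, 13 and 16 give weeks 6, 12, 18, 27, 36 and 45. The calendar rule gives 6, 12, 18, then 18 + 9 = 27, 36, 45. The rules agree exactly.

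**2. Add delay to the cycle rule only.**

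| Delay pattern | Cycle-rule scan weeks | Weeks behind calendar | Calendar date inside the 7-day window? |
|---|---|---|---|
| None | 6, 12, 18, 27, 36 | 0 | Yes |
| One 1-week delay before Cycle 3 | 7, 13, 19, 28, 37 | 1 throughout | Yes, just |
| One 14-day delay before Cycle 3 | 8, 14, 20, 29, 38 | 2 throughout | No |
| 1 week in every cycle | 8, 16, 24, 36, 48 | 2, 4, 6, 9, 12 | No |

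The window runs only backwards from Day 1. If D is cumulative delay in days, the earliest permitted cycle-rule date is D − 7 days after the calendar date. For D > 7 it is later than the calendar date, so no date meets both rules.

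**3. Effect on the recorded progression date.** Recorded date = first scan at or after true progression. For scan times t₁ < t₂ < … with t₀ = 0, mean recorded date = Σ tⱼ[S(tⱼ₋₁) − S(tⱼ)], where S(t) = 2^(−t/m). The exponential form and the range of medians m are assumptions; the documents give neither. Scans are placed on Day 1 itself, and extra scans for clinical reasons are ignored.

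| Assumed median m (weeks) | Mean recorded date, calendar | One 1-week delay | One 14-day delay | 1 week in every cycle |
|---|---|---|---|---|
| 8 | 15.2 | +0.2 | +0.5 | +1.1 |
| 11 | 19.6 | +0.2 | +0.4 | +1.1 |
| 13 | 22.6 | +0.1 | +0.3 | +1.1 |
| 17 | 28.4 | +0.1 | +0.2 | +1.2 |
| 26 | 41.6 | +0.1 | +0.2 | +1.2 |

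These shifts are in weeks and apply to delayed patients only.

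**4. Direction at fixed times.** In the same model the recorded median does not always move later. If every cycle slips by 1 week, it goes from week 18 to week 16 when m = 13, but from week 27 to week 36 when m = 26. The SAP landmarks behave likewise. Three months is 3 × 30.4375 / 7 = 13.0 weeks. By then the calendar scans have caught progression up to week 12, and the slipped scans only up to week 8. Six months is 26.1 weeks. By then the calendar scans have caught progression up to week 18, and the slipped scans up to week 24. Measured PFS in those patients is therefore higher at 3 months and lower at 6 months.

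**The case against.** The strongest reply is that the protocol already says which clock governs. The calendar sentence appears in Section 9.3.14 and in both footnotes, it addresses delays expressly, and the table rows are written in weeks. On that reading the cycle numbers are undelayed labels. This stands as a statement of intent. It does not remove the conflict, because the footnotes still prescribe Day 1 of named cycles and supply a window only for that anchor.

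Several stronger readings are tempting, and the documents do not support them:

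- **Sites will move scans with the dose.** They may. The rows and the calendar sentence point the other way.
- **The shift is large.** Two 14-day delays would move C3D1 from Day 43 to Day 71 (43 + 14 + 14) and the scan to Days 64 to 71, but that is an extreme case. No delay frequency is given, cumulative delay of 7 days or less is absorbed by the window, and clinically indicated scans remain allowed.
- **Late scans lengthen DOR.** DOR starts at first documented response, which a late scan can also postpone. The direction is not established.
- **All delays come from drug toxicity.** The neutrophil and platelet criteria in Section 8.6.2 carry no attribution requirement.
- **The SAP censoring rule will misfire.** In the Day 71 example the scan still precedes the next calendar scan at Day 85 (week 12), so at most one assessment could be called missed. The SAP does not equate late with missed. Two consecutive calendar scans (weeks 12 and 18) fall between cycle-rule scans only under something like a 2-week delay in every cycle (scans at weeks 10, 20, 30).

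It is also fair that PFS, TTP and DOR are secondary, uncontrolled and reported without formal tests.

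**Conclusion.** The conflict is real and operative: past 7 days of cumulative delay, footnotes e and f cannot be followed as written. The text is wrong as it stands and should be corrected, although the consequence is modest.

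Progression is dated later on average in patients with delayed cycles if their site follows the Day 1 wording: about 0.1 to 0.5 week for one delay, and about 1.1 to 1.2 weeks if every cycle slips by 1 week. These sizes rest on the assumed exponential model with medians of 8 to 26 weeks. The effect on a whole cohort would be diluted by undelayed patients and by sites that keep to the calendar; the documents do not allow that share to be estimated.

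A reader might infer that reported PFS is inflated throughout. That is not supported: the mean moves later, but medians and landmark estimates can move either way. The primary ORR is less exposed.

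**What to change.** - **Footnotes e and f:** replace the cycle-anchored visits with nominal weeks from C1D1 (weeks 6, 12 and 18, then every 9 weeks), with a stated window around those weeks. State that scans are not moved when a dose is delayed or held. The width of the window is the sponsor's choice.
- **Section 9.3.14 and the CT/MRI rows of Tables 16.b to 16.e:** replace the switch at the end of Cycle 6 with week 18, its undelayed equivalent, so that the change to 9-weekly scans is also on the calendar. Otherwise a patient slipping 1 week per cycle ends Cycle 6 at week 24 (6 × 28 = 168 days), and the present wording implies a week 24 scan instead of week 27.
- **SAP Section 7.9:** use the same nominal weeks and window to define a missed assessment in the rule on two consecutive missed assessments.

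The cost is wording in an amendment and a line in the SAP. Some scans will no longer fall on a dosing visit. No scans are added beyond the calendar schedule already stated, and no dosing rule changes.

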Appendix B PK Sampling Tables

16.6 Table 16.f Serial PK (Serum) Sample Breakdown: Phase 1b Dose Escalation

Table 16.f Serial PK (Serum) Sample Breakdown: Phase 1b Dose Escalation

	Cycle 1						Cycle 2				Cycles 3-6
	C1D1		C1D2 ^a		C1D3 ^a	C1D4	C2D1 ^a	C2D2 ^a	C2D3 ^a	C2D4 ^a	D1
	Triplicate ECG ^b	PK	Triplicate ECG ^b	PK	PK	PK	PK	PK	PK	PK	PK
Predose (within 30 min before start of infusion)	X3	X1					X1				X
End of infusion (±10 min)	X3	X1					X1				X
1 h after end of infusion (±15 min)	X3	X1					X1				
2 h after end of infusion (±30 min)	X3	X1					X1				X ^c
6 h after end of infusion (±30 min)	X3	X1					X1				
24 h after end of infusion (±1 h)			X3	X1				X1			
48 h after end of infusion (±2 h)					X1				X1		
72 h after end of infusion (±2 h)						X1 ^d				X1 ^d	

CxDx: Cycle x Day x; D: Day; ECG: electrocardiogram; h: hour(s); min: minute(s); PK: pharmacokinetic(s).

When the timing of a PK or safety laboratory blood sample coincides with the timing of ECG measurements, the ECG will be completed before the collection of the blood sample. The triplicate ECG measurements should be completed immediately before the corresponding PK blood draw.

^a Timing of the morning visits should occur at approximately the same time as the morning dosing times on previous days of the cycle. The date/time of the start and end of infusions should be recorded accurately. PK samples should only be collected from the contralateral arm and not from the drug infusion arm.

-
- ^b Triplicate ECGs are collected before PK sample collection. See also Section 9.3.12. Triplicate 12-lead ECG measurements are performed using an ECG recorder. Collection of triplicate ECG begins after patient has rested in supine position for approximately 5 minutes. Each ECG recording of the triplicate ECGs occurs within 3 minutes of each other and over a 10-minute window. When the timing of triplicate and single (safety) ECGs coincide, the site can use the triplicate ECG collection for safety evaluation. The ECG data collected on these ECG recorders can also be used as safety ECGs for assessment on site by investigator (ERT will ensure ECG recorders can transmit ECGs for on-site assessment for investigator). On C1D1, patients will abstain from eating food or having anything to drink except water from a minimum of 2 hours before collection of the predose ECGs until after collection of the 1 hour after end of modakafusp alfa infusion triplicate ECGs. A low-calorie and low-sodium light meal is permitted immediately after the 1-hour postinfusion ECG has been collected. Light meals are permissible immediately after collection of the 2-hour and 6-hour postinfusion ECG timepoints. In patients unable to comply with these recommendations, any food intake should be limited to the smallest required portion of bland food.
- ^c Cycle 4 only for dose escalation phase.
- ^d Only patients receiving modakafusp alfa 0.75 mg/kg or higher.

16.7 Table 16.g Serial PK (Serum) Sample Breakdown: Safety Lead-in Phase of Phase 2 Dose Expansion

Table 16.g Serial PK (Serum) Sample Breakdown: Safety Lead-in Phase of Phase 2 Dose Expansion

	Cycle 1							Cycle 3					Cycle 2, Cycle 4-beyond	
	D1 ^a			D2 ^a		D3 ^a	D4	D1 ^a		D2 ^a	D3 ^a	D4 ^a	D1	
	Triplicate ECG ^b	Modak-af usp alfa PK	Pembro-liz umab PK	Triplicate ECG ^b	Modaka-f usp alfa PK	Modaka-f usp alfa PK	Modaka-f usp alfa PK	Modak-af usp alfa PK	Pembro-liz umab PK	Modaka-af usp alfa PK	Modaka-f usp alfa PK	Modaka-f usp alfa PK	Modaka-f usp alfa PK	Pembro-li zumab PK ^e
Predose (within 30 min before start of infusion)	X3	X1	X					X1	X				X	X
End of infusion (±10 min)	X3	X1	X					X1	X				X	X
1 h after end of infusion (±15 min)	X3	X1						X1						
2 h after end of infusion (±30 min)	X3	X1						X1					X ^c	X ^c
6 h after end of infusion (±30 min)	X3	X1	X					X1	X					
24 h after end of infusion (±1 h)				X3	X1					X1			X ^d	
48 h after end of infusion (±2 h)						X1					X1			
72 h after end of infusion (±2 h)							X1					X1		

CxDx: Cycle x Day x; D: Day; ECG: electrocardiogram; h: hour(s); min: minute(s); PK: pharmacokinetic(s).

CONFIDENTIAL

When the timing of a PK or safety laboratory blood sample coincides with the timing of ECG measurements, the ECG will be completed before the collection of the blood sample. The triplicate ECG measurements should be completed immediately before the corresponding PK blood draw.

- ^a Timing of the morning visits should occur at approximately the same time as the morning dosing times on previous days of the cycle. The date/time of the start and end of infusions should be recorded accurately. PK samples should only be collected from the contralateral arm and not from the drug infusion arm.
- ^b Triplicate ECGs are collected before PK sample collection. See also Section 9.3.12. Triplicate 12-lead ECG measurements are performed using an ECG recorder. Collection of triplicate ECG begins after patient has rested in supine position for approximately 5 minutes. Each ECG recording of the triplicate ECGs occurs within 3 minutes of each other and over a 10-minute window. When the timing of triplicate and single (safety) ECGs coincide, the site can use the triplicate ECG collection for safety evaluation. The ECG data collected on these ECG recorders can also be used as safety ECGs for assessment on site by investigator (ERT will ensure ECG recorders can transmit ECGs for on-site assessment for investigator). On C1D1, patients will abstain from eating food or having anything to drink except water from a minimum of 2 hours before collection of the predose ECGs until after collection of the 1 hour after end of modakafusp alfa infusion triplicate ECGs. A low-calorie and low-sodium light meal is permitted immediately after the 1-hour postinfusion ECG has been collected. Light meals are permissible immediately after collection of the 2-hour and 6-hour postinfusion ECG timepoints. In patients unable to comply with these recommendations, any food intake should be limited to the smallest required portion of bland food.
- ^c Cycle 5 only.
- ^d Cycle 2 only.
- ^e Blood samples for pembrolizumab PK will only be collected at the visits with pembrolizumab dosing (ie, Cycle 1, Cycle 3, Cycle 5, Cycle 7 and beyond).

16.8 Table 16.h Sparse Serum PK Sampling Schedule to Characterize PK of Modakafusp Alfa and Pembrolizumab During Phase 2 Expansion Phase (excluding Safety Lead-In Periods)

Table 16.h Sparse Serum PK Sampling Schedule to Characterize PK of Modakafusp Alfa and Pembrolizumab During Phase 2 Expansion Phase (excluding Safety Lead-In Periods)

	Cycles 1 and Beyond	
	Day 1	
	Modakafusp Alfa PK ^a	Pembrolizumab PK ^c
Predose (within 30 min before start of infusion)	X1	X
End of modakafusp alfa infusion (\pm 10 minutes)	X1	X
2-4 hours after end of modakafusp alfa infusion	X1 ^b	X ^b
Total Timepoints	3	

PK: pharmacokinetic(s).

^a The timing of the morning visits should occur at approximately the same time as previous dosing days. The date/time of the start and end of infusions should be recorded accurately. PK samples should only be collected from the contralateral arm and not from the drug infusion arm.

^b Cycles 1, 3, and 5 only.

^c Blood samples for pembrolizumab PK will only be collected at the visits with pembrolizumab dosing (ie, Cycle 1, Cycle 3, Cycle 5, Cycle 7 and beyond).

